Assessment of the effect of treatment will be based on a non-randomized, open-labeled, prospective study of intravenously administered Omegaven[®] fat emulsion to determine safety and preliminary efficacy in the treatment of PN associated liver injury. This treatment group will be compared to a group based on historical controls, i.e., a subset of patients (those whose direct bilirubin levels was ever > 2 mg/dL) previously studied by Andorsky et al.(31) This study included neonates treated between 1986 and 1996 who depended on parenteral nutrition for at least 90 days after surgical therapy for congenital or acquired intestinal diseases. Our study will primarily follow the patients included in Andorsky et al. study from 2 months before direct bilirubin first reached a level > 2 mg/dL (baseline date) until 2 months after patients either reached 3 consecutive bilirubin levels \leq 2 mg/dL or reached one bilirubin level \leq 2 mg/dL and were weaned from PN died, or underwent a liver transplant. In our exploratory analyses, we will include the entire available follow-up time in Andorsky et al. dataset for each patient.

b. Patient Selection and Inclusion/Exclusion Criteria

Omega-3 Fat Emulsion (Omegaven[®])

After the diagnosis of PNALD is made, patients who are followed by the Clinical Nutrition Service (CNS) or General Surgery Program, in conjunction with the patient's primary physician, will contact [name] or [name] and an evaluation will be performed. Cases may also include referrals of patients with PNALD from other healthcare facilities or self-referrals. If the patient's parents or guardians agree to participate in the study, informed consent will be obtained. The history of present illness and past medical history will be reviewed with the guardian and pertinent demographic and medical information will be recorded on data collection forms. This form will be used to record all laboratory results, nutritional history, and descriptions of any liver biopsies performed.

Though most patients receiving parenteral nutrition do not develop end stage liver disease, there is a small percentage of patients, typically infants and children on prolonged courses of parenteral nutrition, who do go on to develop fulminate liver failure. The study population of this protocol is limited to patients felt to fulfill any one of the following conditions:

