- a) The patient will be PN dependent and at risk for significant hepatic injury due to prolonged use of parenteral nutrition.
- b) Have significant hepatic dysfunction due to parenteral nutrition despite utilization of all conventional therapies.

Inclusion Criteria:

1. Patients will be PN dependent (unable to meet nutritional needs solely by enteral nutrition) and are expected to require PN for at least another 30 days
2. Patients considered eligible for study participation must have parenteral nutrition associated liver disease (PNALD) as defined as a direct bilirubin of ≥ 2 mg/dl or currently on Omegaven through another protocol. Other causes of liver disease should be excluded. A liver biopsy is not necessary for treatment.
3. Direct bilirubin > 2.0 mg/dl, or already on Omegaven through another protocol.
4. Signed patient informed consent.
5. The patient must have utilized standard therapies to prevent the progression of his/her liver disease including surgical treatment, cyclic PN, avoiding overfeeding, reduction/removal of copper and manganese from PN, advancement of enteral feeding, and the use of ursodiol (i.e., Actigall[®]).

Exclusion Criteria:

1. Pregnancy
2. Other causes of chronic liver disease (Hepatitis C, biliary atresia, and alpha 1 anti-trypsin deficiency,)
3. Enrollment in any other clinical trial involving an investigational agent (unless approved by the designated physicians on the multidisciplinary team)
4. The parent or guardian or child unwilling to provide consent or assent

In rare instances, patients diagnosed with PNALD may later be found to have liver disease due to other causes in addition to the use of PN (i.e., inborn errors of metabolism, viral infections). Such causes may not be known at the time of enrollment and will not preclude them from continuing in the study. For the sake of statistical analysis, however, these patients will be excluded although all data will be collected and reviewed.

Screening Procedures

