A second analysis will be done using more contemporary historical controls from patients receiving conventional PN. This will include 50 patients (approximately 10 per year) retrospectively enrolled and previously treated with soybean based emulsions from 1999-2004. Subjects will be selected among patients with surgical gastrointestinal diseases and will have been expected to need PN for 30 days or more at the beginning of PN administration. For the retrospective soybean cohort, to make their selection process comparable to the prospectively enrolled Omegaven® cohort, we will apply the inclusion criteria to the records at moment that cholestasis develops (i.e., direct bilirubin ≥ 2 mg/dL) making no assumptions based upon the outcomes of their actual PN course. Unlike prior analyses comparing Omegaven® treated patients with PNALD with those receiving only soybean fat emulsions, this cohort is expected to be more contemporary with less variability in the standards of care as the study period only covers 4 years rather than 12 year period examined by Andorsky et al. A request for research limited to the use of medical records/charts and computer databases was submitted and approved by the Committee on Clinical Investigations on July 25, 2007. (M07-07-0312).

Inclusion Criteria:

1) Age < 2 years; 2) Be PN dependent (unable to meet nutritional needs solely by enteral nutrition); 3) Present PNALD, as evidenced by two consecutive direct bilirubin ≥ 2.0 mg/dL; 4) Have failed standard therapies to prevent the progression of his/her liver disease that may include surgical treatment, cyclic PN, avoiding overfeeding, reduction/removal of copper and manganese from PN, advancement of enteral feeding, and the use of ursodiol (i.e., Actigall®); 5) At the time the diagnosis PNALD is made, the patient is expected to continue PN at least an additional 30 days.

Exclusion Criteria:

Other known causes of chronic liver disease (hepatitis C, cystic fibrosis, biliary atresia, and alpha 1 anti-trypsin deficiency).

c. Recruitment Methods

Omega-3 Fat Emulsion (Omegaven®)

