Individual patient medical information obtained as a result of this study is considered confidential and disclosure to third parties, other than those cited below, is prohibited. Patient confidentiality will be further ensured by utilizing patient identification code numbers and patient initials. Data generated as a result of this study will be available for inspection, on request by various regulatory agencies. These shall include

all study-relevant documentation, including medical histories to verify eligibility, laboratory test results to verify transcription accuracy, treatment and diagnostic reports, admission/discharge summaries for hospital admissions occurring while the patient is on study, and autopsy reports (if available) for deaths occurring during or in temporal proximity to the study.

As part of the required content of the informed consent, patients must be informed that their records will be reviewed by various regulatory agencies.

Retention of Records

The study coordinator will maintain a comprehensive and centralized filing system of all study related documentation which is suitable for inspection at any time by various regulatory agencies. These include:

- a. Patient files including source documentation and Informed Consent
- b. Study files, including the protocol with all amendments, copies of all regulatory documentation, and all correspondence with the FDA and IRB
- c. Pharmacy files including drug shipment, dispensing, and accountability records, and pharmacy-related correspondence

Per FDA regulations, the Primary Investigator will retain records for a period of five (5) years following discontinuation of the study.

Data Quality and Completeness

Allowable ranges were created for each variable of interest and records outside of those ranges were checked.

c. Data Analysis Plan

Using graphical methods (including boxplots) and descriptive statistics, we will assess assumptions required for validity of statistical methods and presence of outliers. Continuous variables will be summarized via means (and standard deviations) or medians (and interquartile ranges, when appropriate). When appropriate variables will be transformed.

Primary analyses of the primary outcome will be based on the intention-to-treat analysis i.e., patient will be considered receiving either omegaven® or soybean based emulsions throughout the whole follow-up period, regardless of temporary discontinuation of treatment due to infections or other causes.

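### Omegaven patients found after enrolment to have a second liver disease leave the analysis, with no cut-off, outcome-blind judgement, common rule for controls or analysis that restores them

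*Combined protocol and SAP*

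**What the plan says.** Under Patient Selection and Inclusion/Exclusion Criteria, the Omegaven text accepts that "patients diagnosed with PNALD may later be found to have liver disease due to other causes in addition to the use of PN", giving inborn errors of metabolism and viral infections as examples and calling such cases rare. It adds: "Such causes may not be known at the time of enrollment and will not preclude them from continuing in the study". It then states: "For the sake of statistical analysis, however, these patients will be excluded although all data will be collected and reviewed". Late discovery is possible partly because, at entry, "A liver biopsy is not necessary for treatment".

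For the main historical controls, the same section removes patients with incomplete records and those whose direct bilirubin never exceeded 2 mg/dL. It has no exclusion for another liver disease. For the contemporary controls it excludes "Other known causes of chronic liver disease", with examples, and applies the inclusion criteria when cholestasis develops, without regard to the later course.

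Section 5c (Data Analysis Plan) says: "Primary analyses of the primary outcome will be based on the intention-to-treat analysis". It explains the term as treating each patient as on the assigned emulsion "throughout the whole follow-up period, regardless of temporary discontinuation of treatment due to infections or other causes". Under Analysis of Efficacy, patients who die or are transplanted before normalization stay in the primary analysis with an infinite time to event. A comparison analysis leaves those patients out.

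**The concern.** The patients concerned met the entry criteria, still have PNALD and received the study drug. They leave the analysis because of something learned after treatment began. The study is a "non-randomized, open-labeled, prospective study", so whoever orders a further work-up can see how the bilirubin is moving. A child who stays cholestatic is the more natural candidate for a renewed search for other causes. That is an inference, but nothing in the plan guards against it.

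The exclusion is worded for statistical analysis in general. It therefore reaches the primary time-to-normalization comparison, the transplant and mortality comparisons, and the safety outcomes. If those removed are mainly patients who did not normalize, died or were transplanted, the Omegaven group looks better than it was. Potential Study Limitations does not mention this. It argues that differences in severity would understate the effect, whereas this exclusion could overstate it.

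**Working it through.** **Setting the provisions side by side**

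- *Timing.* The Omegaven exclusion acts on information found after enrolment, with no end date. An inborn error of metabolism is present before baseline by nature; a viral infection may be acquired during follow-up. The rule does not separate them.
- *Controls.* The main cohort has no counterpart. The contemporary cohort has a partial one: known causes only, with no clause on later discovery and no stated time limit.
- *Intention-to-treat.* The plan's explanation fixes the treatment label through temporary interruptions. It does not say that every enrolled patient is analysed, so both provisions can be followed literally. The label and the exclusion are simply not reconciled.
- *Deaths and transplants.* The efficacy analysis keeps them as the worst outcome. An Omegaven patient who dies after a late second diagnosis would instead leave the analysis.
- *Sensitivity analyses.* The one that concerns exclusions removes deaths and transplants. None restores the patients at issue.

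**Size**

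The plan gives no sample size, event count or power for the primary efficacy outcome, so there is no stated figure to reproduce. Group sizes of 20, 25 and 30 come from the safety power calculations in section 5d, which also says that enrolment is not based on power. The normalization rates, the number dropped (k) and the premise that every dropped patient is a non-responder are assumptions.

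Apparent proportion = x / (n − k), with x the number normalizing:

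- n = 30, x = 0.60 × 30 = 18: 18/29 = 62%, 18/28 = 64%, 18/27 = 67%, 18/26 = 69% for k = 1 to 4.
- n = 25, x = 0.60 × 25 = 15: 15/24 = 62.5%, 15/23 = 65%, 15/22 = 68%, 15/21 = 71%.

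The primary endpoint is a time to event, so the effect on the log-rank test was simulated. The set-up was no true treatment effect, exponential times, equal groups, a common follow-up length, k non-normalized patients removed from the Omegaven group only, and 3,000 runs per setting. The table gives the percentage of runs with a false significant result favouring Omegaven (nominal 2.5%, half of the two-sided 5%).

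| Per group | Assumed rate | k = 0 | k = 1 | k = 2 | k = 3 | k = 5 |
|---|---|---|---|---|---|---|
| 20 | 40% | 2.8 | 3.6 | 6.2 | 6.9 | 14.8 |
| 20 | 60% | 2.2 | 5.0 | 6.9 | 11.7 | 27.0 |
| 30 | 40% | 2.6 | 3.2 | 4.1 | 5.3 | 9.4 |
| 30 | 60% | 3.2 | 3.8 | 5.9 | 9.3 | 17.0 |

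The simulation error near the nominal level is √(0.025 × 0.975 / 3000) = 0.3 percentage points. With 30 per group, a single exclusion is hard to tell from that noise. The largest single-exclusion shift is 2.2% to 5.0%, with 20 per group and 60% normalizing. With nobody removed, the two-sided rate is 4.7-5.8%, close to nominal.

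**The case against.** The strongest defence is that this is a pre-specified correction of eligibility. Other causes of liver disease are meant to be ruled out at entry, and a child with an inborn error of metabolism had it all along. The rule goes by cause, not response; such cases are called rare; and the data are kept, so results could be reported both ways. The laboratory schedules test more often while bilirubin is high, but list no metabolic or viral work-up, so nothing shows that non-responders are searched harder. Four of 30 is 13%, which strains the word rare.

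Much of this stands, and it rules out three stronger readings. A reader might infer that the exclusion contradicts the intention-to-treat rule; the plan's own narrow explanation of that term does not support this. A reader might infer that the plan removes treatment failures; it does not say so. A reader might also infer that neither control group faces any such exclusion. The contemporary controls have a similar one, and a full-chart review could remove some of them for a later diagnosis too. The clear asymmetry is with the main historical cohort.

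The defence does not answer the missing cut-off, the causes that may arise after baseline, the lack of outcome-blind judgement, or the lack of any planned analysis with these patients included. Keeping the data makes that analysis possible; the plan does not commit to it.

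**Conclusion.** The concern holds as an unreconciled post-enrolment exclusion that can bias the comparison toward Omegaven. It does not hold as a literal contradiction or as evidence that failures will be removed.

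The size depends on how many patients are excluded and on their outcomes, neither of which the documents give. At 30 patients and 60% normalizing, one exclusion moves the proportion by about 2 points. Three non-responders removed raise the false-positive rate favouring Omegaven from 3.2% to 9.3% at 30 per group, and from 2.2% to 11.7% at 20. These are worst cases. If the patients removed resemble those retained, the bias is small. The change is worth making because the groups are small and non-randomized, and because the Omegaven patients' data will exist anyway.

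**What to change.** Define the primary analysis set in every group by the same rule, using only information available at baseline: the start of treatment for Omegaven, and the date of reaching the bilirubin threshold for controls. Keep Omegaven patients with later-found causes in that set. The common rule has to govern the primary analysis as well as any sensitivity analysis. Otherwise, keeping such Omegaven patients while dropping contemporary controls for causes found later would create the reverse imbalance.

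Show the exclusion only as a sensitivity analysis, with one chart definition for all groups, applied without knowledge of outcome where feasible. Report how many patients it removes, from which group, and their outcomes. State in section 5c who is in the intention-to-treat set, and add this source of bias to Potential Study Limitations.

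For the Omegaven group the cost is wording, since the data are collected in any case. The documents do not say whether the main historical dataset records other liver diseases; if it does not, a chart check is needed, or a statement that the rule could not be applied there. The statistical downside is a slightly more diluted effect estimate if patients with a second liver disease respond less well.

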All patients receiving parenteral nutrition are followed by the Clinical Nutrition Service. Eligibility for the trial will be discussed on rounds. Prior historical and physical information, imaging studies, biopsies, and other available specialized tests will be reviewed by the multidisciplinary team experienced in the diagnosis and treatment of parenteral nutrition associated liver disease. Additional biochemical monitoring will be performed as necessary. If the patient's status supports consideration of treatment, the option for non-experimental therapy will be investigated. A similar process will be utilized for self-referrals and potential patients referred from distant healthcare facilities.

Soybean based Fat Emulsion (Intralipid[®] and/or Liposyn[®])

The conventional PN comparison group will be selected from patients previously studied by Andorsky et al.(31) We will study the subset of those patients whose recorded direct bilirubin was ever > 2 mg/dL. Information about these patients will be extracted from the Excel database used for this study and provided to us by the study's Principal Investigator, [name]. A request for research limited to the use of medical records/charts and computer databases was submitted and approved by the Committee on Clinical Investigations on January 17, 2007 (M07-01-0030).

Inclusion Criteria:

Andorsky et al. reviewed medical records of patients who were born at Children's Hospital Boston from 1985 to 1996 and who received a diagnosis of short bowel syndrome at most 30 days after birth (in the neonatal period). Short bowel syndrome was defined as dependence on PN for at least 90 days for diagnosis resulting from congenital intestinal malformations and/or intestinal resection.

Exclusion Criteria:

Patients with incomplete medical records (10 patients briefly seen for a second opinion) were excluded from the Andorsky et al. study. For our study, we will further exclude the subset of patients whose direct bilirubin was never > 2 mg/dL at any time during their follow-up times.

Follow up Study Utilizing Contemporary Historical Controls

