Additional comparisons across treatment periods for subjects receiving Omegaven® will be aimed to assess occurrence of spontaneous bleeding (e.g., unexplained bruising, oozing from gums/incision sites), and maximum triene/tetraene ratio, minimum platelets, and maximum international normalized ratio (INR), trends in pre-albumin (age standardized levels). We will also explore trends in coagulopathies based on curves of platelets, prothrombin time (PT), partial thromboplastin time (PTT) over time, and INR. We will also describe the rate with which INR ratios were > 2 (number of days/follow-up time), as a marker of coagulopathies.

Additional comparisons between Omegaven® and soybean oil fat emulsion groups will be performed with regards to rate in which albumin is > 3 g/dL, maximum triglyceride level, rate of blood stream infections (number of positive blood cultures/follow-up-time under PN after baseline), rate of central venous catheter (CVC) infections (number of CVC infections/follow-up time and number of gram positive CVC infections/follow-up time), and occurrence of anaphylactic reactions after baseline.

Nutritional outcomes between Omegaven® and soybean oil fat emulsion groups that will be compared include changes in weight- and height-for-age Z-scores from baseline to 10% PN or cessation of PN..

We will describe trends over time for all outcomes associated with fatty acid profiles (including triene/tetraene ratios, triglycerides, total omega-6 fatty acids, total omega-3 fatty acids, total saturated, total monounsaturated, and total polysaturated fatty acids). Specific fatty acids such as arachidonic, palmoleic, palmitic, oleic, stearic, and linoleic fatty acids will also be evaluated and described. Also, for exploratory purposes, we will compare the trend in weight- and height-for-age Z-scores between both groups.

2. Omegaven®

3. The patient will complete treatment with Omegaven® in this study when he/she is completely off PN, develops a contraindication for further use, or the patient/family requests to be removed from the study.

f. Data Collection Methods, Assessments and Schedule

Omega-3 Fat Emulsion (Omegaven™)

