Analysis of Baseline Characteristics

For statistical purposes, baseline values will be defined as the last measurement before starting to administer Omegaven® for patients, in the treatment group, and as the measurement taken when a patient first had a direct bilirubin level > 2 mg/dL recorded, in the historical control group. Descriptive statistics for all baseline relevant risk factors will be summarized for Omegaven® (omega-3 based fat emulsion) and historical control (soybean oil fat emulsion) groups. Associations between categorical predictors and Omegaven® vs. soybean oil fat emulsion groups will be tested through chi-square tests. Associations between continuous predictors and treatment groups will be studied through means (and standard deviations) and t-tests, or medians (and interquartile ranges) and Wilcoxon tests, when appropriate.

Analysis of Safety and Tolerability of Omegaven®

All primary safety and tolerability analyses will be based on descriptive statistics. In secondary analyses, we will also assess the statistical significance of differences. Some safety and tolerability outcomes will be measured only in the Omegaven® group. For those, we will compare results before starting PN with Omegaven® (while receiving PN with soybean oil fat emulsions) with after starting PN with Omegaven®. The period receiving Omegaven® will start to be counted 30 days after beginning PN with Omegaven® for the main analysis. Outcomes measured in the Omegaven® and soybean oil fat emulsion groups will be described separately for each of those groups for a period starting 30 days after baseline, i.e., 30 days after starting PN with Omegaven®, for the treatment group, and 30 days after bilirubin > 2 mg/dL, for the soybean oil fat emulsion group.

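### Primary historical controls need not be on PN at their baseline date, whereas Omegaven patients must be; the gap concerns only controls whose bilirubin first exceeds 2 mg/dL late in PN or after weaning

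*Combined protocol and SAP*

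**What the plan says.** The eligibility rules are under Patient Selection and Inclusion/Exclusion Criteria (section b).

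- **Omegaven group.** Criterion 1 requires patients to be PN dependent "and are expected to require PN for at least another 30 days".
- **Primary historical controls.** These come from an earlier neonatal short bowel cohort: "We will study the subset of those patients whose recorded direct bilirubin was ever > 2 mg/dL". The matching exclusion reads: "we will further exclude the subset of patients whose direct bilirubin was never > 2 mg/dL at any time during their follow-up times". The source cohort brings its own PN condition: "Short bowel syndrome was defined as dependence on PN for at least 90 days".
- **Second control cohort (1999-2004).** PN dependence and an expected 30 further days of PN are both required when cholestasis is diagnosed. The stated purpose is "to make their selection process comparable to the prospectively enrolled Omegaven® cohort".

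Section 5c (Analysis of Baseline Characteristics) defines the control baseline "as the measurement taken when a patient first had a direct bilirubin level > 2 mg/dL recorded". The design text and the Additional Predictors of Interest text give the same date. None of the three mentions PN status.

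**The concern.** The 90-day rule describes the length of the PN course, not whether the child was on PN when bilirubin first passed 2 mg/dL. Read literally, the rules admit a control whose first high value came at the end of PN or after weaning. An Omegaven candidate in that position would fail criterion 1.

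Such a control is no longer receiving the comparator emulsion, or soon will not be. Yet section 5c treats every patient as receiving the assigned emulsion for the whole follow-up. Section e also counts a single value at or below 2 mg/dL as normalization once the patient is weaned, so an already weaned control needs one value where a patient still on PN needs three. The listed adjustment covariates include neither PN status nor PN duration.

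Safety is touched as well. Between-group safety follow-up starts 30 days after baseline. For triglycerides above 400 mg/dL and for catheter infections, a control weaned by then contributes only time off the emulsion.

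**Working it through.** The plan gives no figure to reproduce here. The check has three steps.

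**1. Entry rules side by side**

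| Condition at baseline | Omegaven | Primary controls | Second controls |
|---|---|---|---|
| PN dependent | required | not stated | required |
| At least 30 more days of PN expected | required | not stated | required |
| Realized PN course of at least 90 days | not required | required | not required |

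**2. Reach of the 90-day rule**

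Assume one continuous PN course of at least 90 days, and let d be the PN day of the first value above 2 mg/dL.

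- d up to 90 - 30 = 60: the child is on PN and has at least 30 further days of it.
- d from 61 to 90: the child is on PN, but 30 further days are not guaranteed.
- d above 90: neither is guaranteed.

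The gap in PN status is therefore confined to first values after day 90, and the gap in expected duration to those after day 60. Values after weaning could be in the data. The soybean text says that patients at risk were typically followed for several months after PN stopped, and section f says that the source data included outpatient visit notes. The documents do not say how many controls, if any, had a first value that late.

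**3. Illustration of size**

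All inputs are assumed: exponential times to normalization, median 20 weeks, 52 weeks of follow-up, no drug effect, and a share f of controls normalizing at three times the hazard.

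- Rate: λ = ln 2 / 20 = 0.0347 per week.
- Proportion not yet normalized, Omegaven: S_T(t) = exp(-λt).
- Proportion not yet normalized, controls: S_C(t) = (1 - f) exp(-λt) + f exp(-3λt).
- With event densities g_T = -dS_T/dt and g_C = -dS_C/dt and equal group sizes, the large-sample Cox hazard ratio θ solves ∫₀⁵² [g_T - (g_T + g_C) θS_T / (θS_T + S_C)] dt = 0.

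| Share of controls affected | Hazard ratio, Omegaven vs control (truth 1.0) |
|---|---|
| 0% | 1.00 |
| 2% | 0.98 |
| 5% | 0.96 |
| 10% | 0.92 |
| 20% | 0.85 |
| 30% | 0.78 |

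With a true hazard ratio of 2.0 (replace S_T by exp(-2λt)), the same equation gives about 1.8, 1.7 and 1.5 at 10%, 20% and 30%. The affected share here pools controls already off PN with those about to wean.

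**The case against.** The strongest reply is that the plan presupposes PN at baseline. It calls these patients the conventional PN comparison group, its primary hypothesis concerns patients receiving conventional emulsions, and weaning is one of the conditions that end control follow-up. On that view a sentence is missing, and nobody intends to admit weaned children. This is plausible, and it is why a clarification may be enough. But the operative rule admits a value at any time in follow-up, and an analyst applying it would have no ground to remove a weaned child.

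Three stronger readings are tempting, and the documents do not support them.

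- **That the control group does contain weaned children in material numbers.** No count is given. Zero is compatible with the text, and at a share of 2% the distortion is negligible.
- **That the mismatch must dilute or hide an Omegaven effect.** This component would probably pull that way. But controls are also selected on a realized 90 days of PN, which leaves out children weaned earlier who might have resolved quickly. That pushes towards Omegaven, and the documents do not allow the two to be netted.
- **That the bloodstream infection rate is biased.** Its denominator is "number of positive blood cultures/follow-up-time under PN after baseline". A control with no PN time adds no person-time to a pooled Poisson rate, so this alone does not bias it. Only a per-patient rate would be undefined or unstable.

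The one-value route to normalization also appears in section e and in the design text, but not in the efficacy analysis of section 5c, which uses three consecutive values. If section 5c governs, that advantage for weaned controls disappears.

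The second control cohort and the stated limitation on comparability mitigate the problem. Neither addresses PN status in the primary cohort. Some text just before the design section was not available for review, so a condition stated there cannot be ruled out; the eligibility section itself contains none.

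**Conclusion.** The point stands as a gap in the eligibility and baseline rule for the primary control cohort. The plan imposes PN dependence and expected further PN on the Omegaven group and on the second control cohort, but states neither for the controls in its main comparison. Assuming one continuous PN course, the exposure is limited to controls whose first value above 2 mg/dL falls after PN day 90 (PN status) or after day 60 (30 further days).

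The size is unknown. The hazard ratios above rest wholly on assumed inputs, and they exceed the bias that the main fix would remove, because that fix takes out only the controls who are off PN. This component alone would probably work against Omegaven on efficacy; the net direction is not established. The change is worth making because the rule as written can be followed to a result that the plan does not intend, and correcting it is cheap.

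**What to change.** In section b, define eligibility and baseline for the primary controls as the first direct bilirubin above 2 mg/dL recorded while the patient is receiving PN. Exclude controls with no such value. Carry the same definition into the design text, the Additional Predictors text, section e and section 5c. Report how many controls are excluded and how many have their baseline re-dated; if both counts are zero, the question is closed.

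Do not rebuild the expected 30 days from the observed PN course, since that conditions on what happened after baseline. For controls about to wean, add a sensitivity analysis with a day-30 landmark in both groups: leave out patients who stopped PN within 30 days of baseline, and start follow-up at day 30 among those still at risk.

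The cost is one eligibility sentence, its repetition where baseline is defined, and one sensitivity analysis. Section f says that nutritional intake in the source cohort was abstracted at two-week intervals, so PN status at baseline should be recoverable to about that precision. The downside is the possible loss of a few controls from a small cohort.
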